Pre-Exposure Prophylaxis (PrEP) has demonstrated high efficacy, but uptake has been low among YMSM. The iPrEx trial, in which half the participants were under 25, demonstrated an estimated >90% PrEP efficacy among MSM with detectable drug levels in blood.^{28,29} Despite these results, there have been myriad challenges to increasing PrEP uptake in the US, including low awareness, concerns about side effects, low risk perception, and PrEP stigma.³⁰⁻³³ According to national prescription data, youth under 24 are the least likely to initiate PrEP, with only 9% of PrEP initiations in 2015 occurring in this age group.³⁴ In a recent national survey, only half of YMSM aged 15-24 had heard of PrEP, and 1.7% had ever used PrEP.³⁵ Demonstration projects also highlight challenges with PrEP uptake. In the US Demo Project of 550 MSM, only 20% were age 25 or under, and PrEP uptake was lower among younger, non-white, and less educated persons. Self-perceived risk was low among those declining PrEP, despite high rates of condomless sex and STIs in this group.³⁶ In the ATN 110 study of YMSM aged 18-22, PrEP uptake was only 16%, and PrEP adherence was lower among Black YMSM and declined overall during follow-up, particularly with less frequent visits.³⁷ Taken together, these data point to deficits in self-perceived risk which may result in low PrEP uptake, especially among YMSM of color, and the importance of engaging youth when offering and delivering PrEP.

Mobile technologies have enormous potential to reach and engage YMSM in HIV prevention.³⁸⁻⁴² Mobile phones have nearly reached saturation among youth, making mobile technology a particularly promising tool to reach this population that has been traditionally hard to reach through clinical services. Smart phone adoption is particularly high among young adults, with approximately 86% of those under age 30 owning a smart phone. Youth are more likely to use their mobile devices for more activities, such as downloading mobile apps, Internet access, social networking, and accessing health

information.^{43,44} The expansion of smart phones has increased the possibilities of dynamic, mobile phone-based HIV prevention interventions.

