4.0 SELECTION AND ENROLLMENT OF STUDY PARTICIPANTS

4.1 Inclusion Criteria

- Age 15 to 24 years
- Assigned male sex at birth and male identified
- Self-report being HIV uninfected or HIV status-unknown at screening
- Self-report having not had an HIV test in the past 3 months (for Aims 2 and 3 only)
- Self-report not currently taking PrEP (for Aims 2 and 3 only)
- Participants ages 15-18: self-report at least one episode of anal intercourse with a male or transfemale partner during the last 6 months
- Participants ages 19-24: self-report evidence of high risk for acquiring HIV infection including at least one of the following:
 - at least one episode of condomless anal intercourse with an HIV-infected or unknown HIV status male or transfemale partner during the last 6 months; or
 - anal intercourse with 2 or more male or transfemale sex partners during the last 6 months; or
 - exchange of money, gifts, shelter, or drugs for anal sex with a male or transfemale partner during the last 6 months; or
 - sex with a male or transfemale partner and has had an STI during the last 6 months.
- Able to understand, read, and speak English
- Owns an iOS or Android mobile phone
- Willing and able to attend an in-person baseline study visit in the Tampa or Chicago area.

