5.3 Randomization Procedures

Randomization will be used only for the pilot RCT. Only participants who express interest in using LYNX, meet eligibility criteria, provide informed consent, and complete a baseline assessment will be eligible for randomization. Subjects will be randomized 2:1 into either the LYNX intervention arm (N=40) or control arm (N=20).

The 2:1 allocation will allow us to efficiently gather additional data on app utilization. Randomization will be based on a pre-generated list created by the Analytic Core, with random blocks of size three or six, and stratified by site (Tampa, Chicago) and age (15-18, 19-24). After consent and baseline survey completion, the participant will be randomized (assigned to the next available random allocation). **LYNX Intervention Condition:** Individuals who receive LYNX will be given brief instructions on the purpose of the app, how to access it, and an overview of how to use it. Participants will be encouraged to explore all components of the app and use it routinely. **Standard of Care Condition:** Following screening, participants in both conditions will receive standard of care prevention material consisting of provision of information regarding recommendations for HIV testing and referrals to local HIV testing sites and prevention services.

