10.1.3 Pilot RCT (Aim 3)

Response rates to follow-up surveys will be tabulated by recruitment venue and respondent characteristics to help understand potential sources of bias. We will characterize the study population using descriptive statistics and compare the intervention and control groups at baseline using t-, Wilcoxon, and chi-square tests. Point estimates for mean SUS score ≥ 50 and for proportion accessing the app >0.60 will be considered the minimum criteria for acceptability and feasibility, consistent with industry standards.^{49,50} A secondary feasibility outcome will be achieved if $\geq 50\%$ of participants who open the app complete their personalized risk score at least once.

The secondary outcomes of preliminary efficacy of the LYNX app to increase HIV/STI testing (any testing over follow-up) and PrEP uptake (as described above) will be evaluated using unadjusted risk ratios for each outcome. If there is evidence of divergence from balance in measured baseline covariates (i.e., failure of randomization), post-hoc analyses using Poisson regression with robust standard errors will be used to estimate adjusted risk ratios. Outcome variables will represent any HIV testing and any PrEP uptake over the follow-up period. Separate models will be estimated for each outcome.⁵²

With 60 participants randomized 2:1 to intervention: control, and 10-20% attrition, we will have 80% power to detect 37-42 percentage point increases in HIV testing and PrEP uptake, depending on rates in controls. The lack of precision and large minimum detectable effects, typical of pilot studies, will entail careful interpretation of study results in the light of overall patterns, plausibility, and findings from other mHealth studies.

Qualitative data from exit interviews will be analyzed by the LYNX team using the methods described in Aim 1 and will inform efforts to finalize app revisions and prepare for efficacy evaluation of the app.

Note: Any deviations from the analysis plans outlined above or in the sections that follow will be documented and justified in the Statistical Analysis Plan developed for this protocol.

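### Randomisation is stratified by site and age group, but the efficacy analysis ignores both and adjusts only on an undefined imbalance trigger that they would almost never set off

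*Combined protocol and SAP*

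**What the plan says.** Section 5.3 describes a pre-generated 2:1 list in random blocks of 3 or 6, "stratified by site (Tampa, Chicago) and age (15-18, 19-24").

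Section 10.1.3 says that the secondary efficacy outcomes, HIV/STI testing and PrEP uptake, "will be evaluated using unadjusted risk ratios for each outcome". Adjusted ratios are conditional: "If there is evidence of divergence from balance in measured baseline covariates (i.e., failure of randomization), post-hoc analyses using Poisson regression", with robust standard errors. The section does not say what counts as evidence of imbalance or which covariates would enter. It lists baseline t, Wilcoxon and chi-square tests, but gives no significance level and does not tie them to the condition. No section puts site or age group into an efficacy model.

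The closing note of 10.1.3 says: "Any deviations from the analysis plans outlined above or in the sections that follow will be documented and justified in the Statistical Analysis Plan". That covers departures from the plan. It does not promise a threshold or a covariate list.

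On whether age might predict outcome, section 1.1 reports a PrEP demonstration project in which "only 20% were age 25 or under, and PrEP uptake was lower among younger, non-white, and less educated persons". Section 4.1 admits the two age groups on different risk criteria: "Participants ages 15-18: self-report at least one episode of anal intercourse with a male or transfemale partner during the last 6 months", against "Participants ages 19-24: self-report evidence of high risk for acquiring HIV infection including at least one of the following".

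**The concern.** Two things do not fit together.

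- **The design and the analysis differ.** The trial stratifies on two factors and then analyses as if it had not. The trigger cannot repair this, because factors balanced by design will not look imbalanced. It responds to everything except the stratification factors.
- **The adjusted ratio is open.** With no threshold and no covariate list, two analysts following 10.1.3 faithfully could disagree on whether to adjust and for what. The parenthesis in the quoted condition also treats imbalance as a sign that randomisation failed. Under a valid list, imbalance is chance.

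At stake are some precision in the efficacy estimates, if site or age group predicts outcome, and an unambiguous adjusted result.

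**Working it through.** **1. The plan's own figure.** Section 10.1.3 states: "10-20% attrition, we will have 80% power to detect 37-42 percentage point increases in HIV testing and PrEP uptake". Attrition of 10% leaves 18 control and 36 LYNX participants; 20% leaves 16 and 32. A two-sided 5% test is assumed, since no level is stated. With pooled proportion p̄,

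power = Φ{[d - 1.96·√(p̄(1-p̄)(1/n0+1/n1))] / √(p0(1-p0)/n0 + p1(1-p1)/n1)}.

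- Example: n0=18, n1=36, p0=0.15, p1=0.52, so p̄=(2.7+18.72)/54=0.397. Power = Φ[(0.37-0.277)/0.118] = 0.784.
- Solved for 80% power over control rates of 10-50%, the detectable difference is 35.9-39.2 points at 10% attrition and 37.6-41.5 at 20%.

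The stated 37-42 points reproduces as a range over attrition and control rate.

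**2. Can site or age group set off the trigger?** Complete blocks are exactly 2:1, so only an unfinished block can disturb a stratum. The worst case is a block of 6 that has issued four LYNX slots (4 - 4×2/3 = +4/3) or two control slots (0 - 2×2/3 = -4/3).

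- A site spans two age strata, so its LYNX count lies within 8/3 of two-thirds of its size.
- With 30 per site (assumed), the extreme is (20+8/3)/40 = 56.7% against (10-8/3)/20 = 36.7%, a gap of 20 points.
- The standard error is √(0.25×(1/40+1/20)) = 0.137, so chi-square = (0.20/0.137)² = 2.1. That is below 3.84 (5% level) and 2.71 (10% level).

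Simulation agrees. In 20,000 stratified randomisations a 5% test flagged site or age group in none, and in 0.06% among completers at 20% attrition. Across four assumed site and age mixes the rate was 0 to 0.005%. At the 10% and 20% levels it was 0 of 10,000 each. Without stratification the rates would be 10.3%, 20.2% and 37.1% at the three levels. One unstratified binary covariate was flagged in 5.3%. A significance-test trigger is an assumption, since 10.1.3 names none.

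**3. What stratifying changes.** For stratum k, with a and b events among n1 LYNX and n0 control participants, N = n1+n0 and m = a+b:

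- Mantel-Haenszel (MH) ratio = Σ(a·n0/N) / Σ(b·n1/N).
- CMH statistic = [Σ(a - n1·m/N)]² / ΣV, where V is the hypergeometric variance.

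Simulation: 10,000 trials per scenario, four equally likely strata, +37 points in every stratum. Control rates are assumptions: 35% throughout, 20/30/40/50%, or 10/25/45/60%. Monte Carlo error is about 0.5 point per figure. Power (%), unstratified v stratified:

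| Control rates | Attrition | Chi-square v CMH | Wald ratio v MH ratio |
|---|---|---|---|
| 35% in all | 10% | 76.0 v 74.8 | 62.6 v 62.1 |
| 35% in all | 20% | 70.2 v 68.4 | 54.6 v 53.8 |
| 20-50% | 10% | 75.9 v 77.0 | 62.4 v 64.3 |
| 20-50% | 20% | 70.6 v 71.2 | 54.4 v 56.1 |
| 10-60% | 10% | 77.5 v 82.5 | 62.7 v 70.3 |
| 10-60% | 20% | 71.8 v 76.8 | 54.3 v 62.0 |

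The formula in step 1 gives Φ[(0.37-0.278)/0.135] = 0.753 for the first chi-square cell, close to the simulated 76.0. A repeat with 6,000 trials gave 70.8 v 68.8 for CMH at equal rates and 20% attrition. With ages 15-18 only a quarter of the sample, the changes at 10% then 20% attrition were:

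- CMH: -1.3 and -1.6 (equal rates), +4.4 and +4.9 (10-60%).
- MH ratio: -0.3 and -1.2 (equal rates), +7.5 and +7.6 (10-60%).

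**4. False positives.** Null rejection (%) at 10% attrition for equal, 20-50% and 10-60% rates was: chi-square 5.4, 4.8, 3.6; CMH 5.1, 5.5, 4.9; Wald ratio 3.9, 3.2, 2.6; MH ratio 4.0, 4.0, 4.1. The unadjusted tests grow conservative as the strata become prognostic.

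**5. PrEP-like control rates.** Wald v MH ratio power (assumed rates, 5,000 trials, 10% attrition, +37 points): 16% in all strata, 59.8 v 59.3; 8-24%, 61.0 v 61.0; 4-30%, 60.0 v 62.5; 5% in all, 32.2 v 31.4; 1-10%, 32.2 v 32.3.

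**6. Sparse PrEP events.** With no effect and 18 v 36 completers, the chance that an arm has no events is 1 - [1-(1-p)^18][1-(1-p)^36]. This is about 5% at p=16%, 49% at 5% and 88% at 1.7%. The 16% and 1.7% are uptake and ever-use figures from section 1.1, used as assumptions; 5% is assumed. Neither the unadjusted nor the MH ratio is usable in those trials.

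**The case against.** The strongest reply is that nothing here is wrong. The unadjusted ratio is fixed in advance and leads, and the adjusted one is openly labelled post hoc. Stratified factors staying balanced is the design doing its job. What remains is efficiency, in secondary outcomes of a pilot whose own plan warns that they are imprecise. Most of this stands, and it limits the point to a minor one.

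The evidence that the strata matter is also thin. The demonstration project was mostly over 25, so it gives no rates for 15-18 against 19-24. Different entry criteria show different risk, not different testing or uptake. Nothing suggests that site is prognostic. The one scenario with a clear gain puts a stratum at 60+37 = 97% in the LYNX arm. For PrEP, the outcome the age evidence concerns, step 5 shows little or no gain. All of this stands.

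The separate analysis plan could contain a threshold and covariates. That cannot be excluded, but the note in 10.1.3 promises only to record deviations.

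The reply does not remove the mismatch itself: the trigger passes over the two factors the trial chose to control, and the adjusted ratio stays undefined.

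**Conclusion.** The point holds as a minor improvement. Site and age group are stratified in 5.3 and never used in 10.1.3, and the condition for adjusting would essentially never be met by them. It would respond only to chance differences in other covariates.

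Outside the 10-60% scenario, stratifying changed power by about -2 to +2.5 points over all the runs shown. In that scenario it added about 5 points (CMH) to 8 points (MH ratio). These sizes rest on assumed stratum rates, a uniform +37 points and attrition at random. The trigger result concerns age group; age in years could still differ by chance within a stratum.

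A reader might infer more, and the documents do not support it:

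- **That the unadjusted ratio is biased or inflates false positives.** It is unbiased under this randomisation, and step 4 shows it at worst mildly conservative.
- **That the pilot's main conclusions are at risk.** The primary endpoints in 6.3.3, the System Usability Scale score and app opening, do not use this analysis, and section 1.1 makes the next trial depend on feasibility and acceptability.
- **That stratifying would rescue the PrEP comparison.** Steps 5 and 6 show that it would not.

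**What to change.** In 10.1.3:

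- Make the main estimate for each efficacy outcome the Mantel-Haenszel risk ratio stratified by site and age group, with a CMH test.
- Keep the unadjusted risk ratio as a sensitivity analysis.
- Delete the imbalance condition and the parenthesis calling imbalance a randomisation failure. Baseline comparisons can stay as description but should not decide the analysis.
- Name in advance any further covariate to be adjusted for.

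The cost is a few sentences; site and age group are already recorded for randomisation. If the strata are not prognostic, about 1 to 2 points of power are lost. Sparse PrEP events are a separate matter that this change leaves open.

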10.2 Missing Data

Several procedures will be used to conduct data analysis when data for either outcomes or covariates are missing. The first step will be to assess the extent and pattern of missing data. If data are missing for only a few cases, then data analysis will be conducted only on study participants with complete data. However, when such a strategy would result in loss of data from a substantial proportion of participants, or if this approach would lead to biased or inaccurate results, then some form of imputation will be performed. The form of imputation used will depend on the nature of the data that are missing. For example, data that are collected repeatedly might be imputed using the “last value carried forward” method; and in some instances, interpolation between neighboring points might also be used.

When the primary endpoint is missing, one data analysis will be conducted using only cases with the endpoint. Subsequent analysis will be done where missing endpoints are imputed. Hot-deck imputation or regression imputation may also be used in this context.

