5.4.3.4 Study Follow-up

All enrolled participants will be followed for 24 weeks. After enrollment, all follow-up visits will occur online, with SMS reminders, email, and phone follow-up conducted as needed to ensure completion of study procedures. Participants will complete an online CASI at 12 and 24 weeks and receive a stipend for completion of procedures at each study visit. Visit windows will be approximately 14 days before/after the target date. Participants will also be able to obtain additional home HIV self-test kits during the study follow-up, if needed. At the 3 month visit, any persons who have a positive HIV test plus up to 20 participants randomized to the LYNX arm will participate in an in-depth interview conducted by UCSF/SFDPH study staff via video-conferencing. The purpose of this interview is to elicit feedback on their experiences using the app, any technical difficulties encountered, and how the app could be further improved. Participants will be selected for interviews using purposive sampling based on level of engagement with the app, whether participants completed HIV/STI testing and/or initiated PrEP during the study, and to achieve diversity based on sociodemographics (e.g. age, race/ethnicity). Additionally, we will offer interviews to all participants who have a confirmed HIV diagnosis. In addition to asking about their experiences using the app, these participants will also be asked about additional information or support that would have been helpful at the time of receiving a positive HIV test result, and their experiences in getting linked to HIV care. By purposively sampling certain participants for the exit interviews, the goal is to select "information-rich cases from which one can learn a great deal about issues of central importance to the purpose of the research."⁵¹ All interviews will be audio recorded for transcription and analysis. Participants will be reimbursed for completion of each study visit according to local study site guidelines.

We will also conduct medical record abstraction for participants in this study. The goal of the medical record abstraction is to explore whether it is feasible to collect more objective measures of HIV and STI

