6.3.3 On-Study evaluations/measures

- *Acceptability*
 - *System Usability Scale: a validated 10-measure scale that assesses subjective usability of a system, or, in this case, an app. It is scored from 0 to 100, and a score of 50 or greater indicates that the app is acceptable**
 - *In-depth interview (qualitative)*
- *Feasibility: app analytics (frequency of logins, use of LYNX app components)*
 - *We will use app analytics to determine whether at least 60% of individuals randomized to the intervention condition opened the LYNX app at least one time after their initial introduction to the app by research staff**
- *App-Specific Measures*
 - *Frequency and duration of app use*
 - *Content and functionalities most and least utilized*
 - *Number of HIV/STI home testing kits, condoms and lube requested*
- *Preliminary efficacy*
 - *HIV and STI testing frequency*
 - *HIV/STI Testing: participants will be asked to self-report on frequency of HIV/STI testing since last assessment. The primary HIV/STI testing measure will be the proportion of participants who self-report at least one test during the follow up period. We will also explore the concordance of self-report with data collected by medical release and using data electronically self-reported in the app, including home testing kits provided by request through the app.*

- *PrEP interest and uptake*
 - *PrEP care linkage: participants will self-report whether, in the past 3 months, they made and attended a clinic appointment for PrEP initiation, whether they were prescribed PrEP, and whether they utilized PrEP. We will also explore the concordance of self-reported prep use with data on PrEP use collected by medical release.*
- *Sexual and drug use behaviors*
- *Access to and utilization of health care*
- *IMB model constructs for HIV/STI testing and PrEP knowledge, attitudes, motivations, and behavioral skills*
- *Eco-social factors influencing uptake of prevention strategies*
- *Potential moderators of the intervention (measured at baseline and follow-up visits)*
 - *Demographics: Age, student status, education level, income, living situation, employment, insurance status, depressive symptoms, anxiety, trauma, and abuse*

*Primary study endpoints

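### The complete-data rule does not fit outcomes of the 'any over follow-up' kind: when week 24 is missing, a week-12 'yes' is final and a week-12 'no' is not (small effect, simple remedy)

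*Combined protocol and SAP*

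**What the plan says.** Section 10.1.3 defines the two secondary efficacy outcomes cumulatively: "Outcome variables will represent any HIV testing and any PrEP uptake over the follow-up period". Each is compared by an unadjusted risk ratio. Section 6.3.3 gives the testing measure as the "proportion of participants who self-report at least one test during the follow up period". The answers come from two surveys (section 5.4.3.4): "Participants will complete an online CASI at 12 and 24 weeks".

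The recall windows differ (section 6.3.3). For testing, "participants will be asked to self-report on frequency of HIV/STI testing since last assessment". For PrEP, "participants will self-report whether, in the past 3 months, they made and attended a clinic appointment for PrEP initiation".

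Section 10.2 makes the complete-data analysis conditional: where few cases have missing data, "data analysis will be conducted only on study participants with complete data". It departs from this if a substantial share of participants would be lost, or "if this approach would lead to biased or inaccurate results, then some form of imputation will be performed". Its example for repeated measurements is last value carried forward. Hot-deck and regression imputation are mentioned only for a missing primary endpoint, and testing and PrEP are not primary.

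The plan does not say whether 'complete' means that the outcome is determined or that both surveys were answered. Nor does it say how a participant with a week-12 answer and no week-24 answer is classified.

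**The concern.** Take two men who miss week 24. The first reported a test at week 12, so his outcome is known to be 'yes'. The second reported none, so his outcome is unknown. There are two ways to apply 'complete data':

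- **Outcome determined.** The first man stays and the second is dropped. Retention then depends on the outcome, and both arms' proportions are too high even if week-24 loss is purely random.
- **Both surveys answered.** Both men are dropped. A known event is discarded, and the estimate is biased if loss depends on the week-12 answer.

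At stake are the testing and PrEP risk ratios. Unequal loss between arms would also move the ratio, and it is plausible because only one arm has an app to engage with.

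**Working it through.** **The plan's own figure.** Section 10.1.3 states 80% power for increases of 37-42 percentage points, with 60 participants randomised 2:1 and 10-20% attrition. It gives neither alpha nor control rates, so I assume two-sided 0.05 and control rates of 10-30%. With power = Φ((d - 1.96·SE0)/SE1), where SE0 is the pooled and SE1 the unpooled standard error, 80% power needs 36.0-39.3 points at 18:36 and 38.5-41.5 points at 16:32. As one case, take 16:32 and 20% v 62%. The pooled rate is 0.48, SE0 = √(0.48·0.52·(1/16+1/32)) = 0.153 and SE1 = √(0.16/16 + 0.2356/32) = 0.132. Power is Φ((0.42-0.300)/0.132) = 0.82. The stated range is consistent.

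**Assumed inputs** (the documents give no event rates). Any event by week 24, p: 0.70 LYNX and 0.40 control. By week 12, p12: 0.50 and 0.20. All week-12 surveys are answered. Week-24 loss is m. The conditional second-interval rates are (0.70-0.50)/0.50 = 0.40 and (0.40-0.20)/0.80 = 0.25. The true RR is 1.75.

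**Reading 1, outcome determined, random loss.** Estimate = [(1-m)p + m·p12] / [(1-m) + m·p12].

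| Loss LYNX / control | LYNX | Control | RR |
|---|---|---|---|
| 5% / 5% | 0.690/0.975 = 70.8% | 0.390/0.960 = 40.6% | 1.74 |
| 10% / 10% | 0.680/0.950 = 71.6% | 0.380/0.920 = 41.3% | 1.73 |
| 20% / 20% | 0.660/0.900 = 73.3% | 0.360/0.840 = 42.9% | 1.71 |
| 10% / 30% | 71.6% | 0.340/0.760 = 44.7% | 1.60 |
| 30% / 10% | 0.640/0.850 = 75.3% | 41.3% | 1.82 |

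The last two rows are illustrative extremes. The 30%/10% row is (12+2)/60 = 23% overall loss, above the planned range. With no true effect, equal random loss leaves the RR at 1.00. With 30% in both arms, a constant hazard, and 20% v 10% loss, the RR is 1.05.

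**Reading 2, both surveys answered.** Under random loss it returns 70% and 40%, but it discards m·(40·0.50 + 20·0.20) = 24m known events: 2.4 at 10% loss and 4.8 at 20%. If week-12 'no' men are lost at 30% and 'yes' men at 10%:

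- LYNX: (0.45 + 0.35·0.40)/0.80 = 73.8%
- Control: (0.18 + 0.56·0.25)/0.74 = 43.2%

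**Last value carried forward, 20% random loss.** Estimate = (1-m)p + m·p12, which gives 0.56+0.10 = 66% and 0.32+0.04 = 36%. The RR is 0.66/0.36 = 1.83.

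**Two-interval estimate.** 1-(1-p12)(1-p24|no) gives 1-0.50·0.60 = 70% and 1-0.80·0.75 = 40%. This holds under random loss and when loss depends only on arm and the week-12 answer. At 20% loss, the per-arm variance of Reading 2 relative to this estimate is:

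- LYNX: 0.21/32 = 0.00656 against 0.36·0.25/40 + 0.25·0.24/16 = 0.00600, a ratio of 1.09
- Control: 0.24/16 = 0.0150 against 0.5625·0.16/20 + 0.64·0.1875/12.8 = 0.0139, a ratio of 1.08

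At 10% loss the ratio is about 1.04.

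**The case against.** A reader might infer that the plan commits to a biased rule whatever the extent of loss. It does not: the rule is conditional on little being missing and gives way where it would bias the result. That stands, but it does not settle the matter. The plan puts no number on 'few', while 10-20% attrition of 60 is 6-12 men. The one method it names for repeated data treats an unresolved week-12 'no' as final.

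A reader might also infer a materially distorted comparison. Under equal random loss the RR moves by only about 0.5-2% at 5-20% loss, and the larger shifts need unequal or answer-dependent loss that is assumed here, not documented. Simulated 40:20 trials under the same assumed rates show how small this is beside the noise. At 20% equal loss the root mean squared error of the risk difference is 0.142 for Reading 1, 0.148 for Reading 2 and 0.142 for the two-interval estimate. On the log-RR scale Reading 1 does slightly better than the two-interval estimate (0.334 v 0.355), despite its bias. Section 10.1.3 already warns about imprecision.

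It would also be wrong to call these risk ratios the trial's only comparative evidence: section 2.2 also compares changes in sexual risk behaviours. The primary endpoints, usability score and app opening (section 6.3.3), are unaffected.

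The early-discontinuation visit (6.3.4), acceptance of out-of-window surveys (7.3.2) and tracing (8.1) reduce missing week-24 data. They do not say how to classify what remains. Medical records need an optional release and serve only to explore concordance.

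**Conclusion.** The concern holds as a small, avoidable defect in two secondary outcomes. Under the assumed rates, keeping only determined outcomes overstates each arm by under 1 point at 5% equal random loss and by about 3 points at 20%, against a detectable effect of 37-42 points. Requiring both surveys is unbiased under random loss and costs 4-9% in per-arm variance at 10-20% loss. It is biased when loss depends on the week-12 answer. Loss of 10% v 30% by arm would bring the RR to 1.60, but nothing in the documents predicts such an imbalance.

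The sizes rest on the assumed event rates and on a week-12 answer from everyone lost at week 24; fewer week-12 answers would shrink them. The gap in the text does not depend on those assumptions. It should be corrected because data already collected support a better estimate, not because it threatens the pilot's conclusions.

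**What to change.** In sections 10.1.3 and 10.2, for these two outcomes:

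- Count a week-12 'yes' as an event whether or not week 24 is answered.
- Estimate each arm's proportion as 1-(1-p12)(1-p24|no). Here p12 uses everyone with a week-12 survey, and p24|no uses week-12 'no' men with a week-24 survey. Equivalently, impute week 24 within arm given a week-12 'no'.
- Use this for the unadjusted risk ratio in place of the complete-data ratio, and do not carry a week-12 'no' forward.
- State the assumption: among week-12 'no' men in an arm, week-24 loss is unrelated to the later outcome. The data cannot test this.
- Add men with only a week-24 survey for testing only, and only if the item as asked reaches back to baseline. The PrEP item covers just the last 3 months.

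**Cost.** Plan wording and a few lines of code, with no new data. When nobody misses week 24 the estimate equals the ordinary proportion.

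**Downsides.**

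- A delta-method or bootstrap interval replaces the simple 2x2 formula.
- With few or no control events, which is likely for PrEP, the ratio may be undefined. At an illustrative 5% rate, 20 controls have a 0.95^20 = 36% chance of no events. The risk difference should therefore be reported as well.
- The estimate can be slightly more variable on the log-RR scale than the biased rule.
- Any adjusted Poisson model would need the imputation version.
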